## 3.0 PATIENT SELECTION

### 3.1 Inclusion Criteria

1. Histologically or cytologically proven metastatic or inoperable pancreatic adenocarcinoma.
2. Measurable disease defined as lesions that can be accurately measured in at least one dimension (longest diameter to be recorded) as  $\geq 10$  mm with CT scan or MRI, as  $\geq 20$  mm by chest x-ray, or  $\geq 10$  mm with calipers by clinical exam.
3. Must have progressed on, been intolerant to, or refused gemcitabine-based therapy.
4. At least 18 years of age.
5. ECOG performance status  $\leq 2$  (see Appendix A).
6. Normal bone marrow and organ function as defined below:
  - a. Absolute neutrophil count  $\geq 1,000/\text{mcl}$
  - b. Platelets  $\geq 100,000/\text{mcl}$
  - c. Total bilirubin  $\leq 2.0$  mg/dL
  - d. Creatinine  $\leq 2.0$  mg/dL
  - e. AST or ALT  $\leq 2.5$  IULN ( $\leq 5X$  IULN if liver metastases are present)
7. Women of childbearing potential and men must agree to use adequate contraception (hormonal or barrier method of birth control, abstinence) prior to study entry and for the duration of study participation. Should a woman become pregnant or suspect she is pregnant while participating in this study, she must inform her treating physician immediately.
8. Able to understand and willing to sign an IRB approved written informed consent document (or that of legally authorized representative, if applicable).

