### 12.2 Disease Parameters

**Measurable disease:** Measurable lesions are defined as those that can be accurately measured in at least one dimension (longest diameter to be recorded) as >20 mm by chest x-ray, as >10 mm with CT scan, or >10 mm with calipers by clinical exam. All tumor measurements must be recorded in millimeters (or decimal fractions of centimeters).

**Malignant lymph nodes:** To be considered pathologically enlarged and measurable, a lymph node must be >15 mm in short axis when assessed by CT scan (CT scan slice thickness recommended to be no greater than 5 mm). At baseline and in follow-up, only the short axis will be measured and followed.

**Non-measurable disease:** All other lesions (or sites of disease), including small lesions (longest diameter <10 mm or pathological lymph nodes with  $\geq 10$  to <15 mm short axis), are considered non-measurable disease. Bone lesions, leptomeningeal disease, ascites, pleural/pericardial effusions, lymphangitis cutis/pulmonitis, inflammatory breast disease, and abdominal masses (not followed by CT or MRI), are considered as non-measurable.

*Note: Cystic lesions that meet the criteria for radiographically defined simple cysts should not be considered as malignant lesions (neither measurable nor non-measurable) since they are, by definition, simple cysts.*

‘Cystic lesions’ thought to represent cystic metastases can be considered as measurable lesions, if they meet the definition of measurability described above. However, if non-cystic lesions are present in the same patient, these are preferred for selection as target lesions.

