**Target lesions:** All measurable lesions up to a maximum of 2 lesions per organ and 5 lesions in total, representative of all involved organs, should be identified as target lesions and recorded and measured at baseline. Target lesions should be selected on the basis of their size (lesions with the longest diameter), be representative of all involved organs, but in addition should be those that lend themselves to reproducible repeated measurements. It may be the case that, on occasion, the largest lesion does not lend itself to reproducible measurement in which circumstance the next largest lesion which can be measured reproducibly should be selected. A sum of the diameters (longest for non-nodal lesions, short axis for nodal lesions) for all target lesions will be calculated and reported as the baseline sum diameters. If lymph nodes are to be included in the sum, then only the short axis is added into the sum. The baseline sum diameters will be used as reference to further characterize any objective tumor regression in the measurable dimension of the disease.

**Non-target lesions:** All other lesions (or sites of disease) including any measurable lesions over and above the 5 target lesions should be identified as non-target lesions and should also be recorded at baseline. Measurements of these lesions are not required, but the presence, absence, or in rare cases unequivocal progression of each should be noted throughout follow-up.

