### **12.3 Methods for Evaluation of Measurable Disease**

All measurements should be taken and recorded in metric notation using a ruler or calipers. All baseline evaluations should be performed as closely as possible to the beginning of treatment and never more than 4 weeks before the beginning of the treatment.

The same method of assessment and the same technique should be used to characterize each identified and reported lesion at baseline and during follow-up. Imaging-based evaluation is preferred to evaluation by clinical examination unless the lesion(s) being followed cannot be imaged but are assessable by clinical exam.

**Clinical lesions:** Clinical lesions will only be considered measurable when they are superficial (e.g., skin nodules and palpable lymph nodes) and  $\geq 10$  mm diameter as assessed using calipers (e.g., skin nodules). In the case of skin lesions, documentation by color photography, including a ruler to estimate the size of the lesion, is recommended.

**Chest x-ray:** Lesions on chest x-ray are acceptable as measurable lesions when they are clearly defined and surrounded by aerated lung. However, CT is preferable.

**Conventional CT and MRI:** This guideline has defined measurability of lesions on CT scan based on the assumption that CT slice thickness is 5 mm or less. If CT scans have slice thickness greater than 5 mm, the minimum size for a measurable lesion should be twice the slice thickness. MRI is also acceptable in certain situations (e.g. for body scans).

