## **12.4 Response Criteria**

### **12.4.1 Evaluation of Target Lesions**

**Complete Response (CR):** Disappearance of all target lesions. Any pathological lymph nodes (whether target or non-target) must have reduction in short axis to <10 mm.

**Partial Response (PR):** At least a 30% decrease in the sum of the diameters of target lesions, taking as reference the baseline sum diameters.

**Progressive Disease (PD):** At least a 20% increase in the sum of the diameters of target lesions, taking as reference the smallest sum on study (this includes the baseline sum if that is the smallest on study). In addition to the relative increase of 20%, the sum must also demonstrate an absolute increase of at least 5 mm. (Note: the appearance of one or more new lesions is also considered progressions).

**Stable Disease (SD):** Neither sufficient shrinkage to qualify for PR nor sufficient increase to qualify for PD, taking as reference the smallest sum diameters while on study.

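### Inclusion criterion 2 admits patients with no measurable lesion under 12.2 and 12.3, so they have no target lesion and cannot be scored PR or target-sum PD

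*Combined protocol and SAP*

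**What the plan says.** Section 3.1, item 2, gives its own definition of measurable disease for eligibility: "Measurable disease defined as lesions that can be accurately measured in at least one dimension (longest diameter to be recorded". The cut-offs that follow are at least 10 mm on CT or MRI, at least 20 mm on chest x-ray and at least 10 mm by calipers. It has no separate rule for lymph nodes, no slice-thickness rule and no reference to section 12.

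Section 12.2 defines the same term differently:
- The general size limits are given "as >20 mm by chest x-ray, as >10 mm with CT scan, or >10 mm with calipers by clinical exam". MRI is not listed there.
- For nodes, "a lymph node must be >15 mm in short axis when assessed by CT scan".
- The non-measurable class is residual: "All other lesions (or sites of disease), including small lesions (longest diameter <10 mm or pathological lymph nodes with" a short axis of 10 to under 15 mm.
- Target lesions come only from the measurable class: "All measurable lesions up to a maximum of 2 lesions per organ and 5 lesions in total".

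Section 12.3 adds: "If CT scans have slice thickness greater than 5 mm, the minimum size for a measurable lesion should be twice the slice thickness".

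In 12.4.1, PR requires "At least a 30% decrease in the sum of the diameters of target lesions", and the numerical PD rule (a 20% increase plus at least 5 mm) uses the same sum. For patients without target disease, the table in 12.4.3 offers CR, non-CR/non-PD, PD or not evaluated, with no PR row. Section 5.5.4 excludes from response evaluation only patients who leave for treatment-related adverse events before completing Cycle 2 without any disease assessment.

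**The concern.** Two rules for the same term conflict, and the looser one controls entry. Section 4.1 requires a completed eligibility checklist at registration. A checklist built from 3.1 would admit a patient whose only lesion section 12 calls non-measurable.

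Such a patient has no target lesion and therefore no route to PR, but still counts in the response denominator. Three analyses are exposed:
- ORR, the first secondary objective (2.2).
- The interim look at response after 10 evaluable phase II patients (14.3), where one patient is a tenth of the sample.
- The logistic models relating biomarkers and genetic alterations to response (14.2), where a patient who could not be scored PR may be read as a biological non-responder.

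For the primary endpoint, progression in these patients rests on new lesions, unequivocal non-target worsening or death, without the 20% sum rule.

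**Working it through.** The plan gives no figure on this point, so there is none to reproduce. The check runs example lesions through both sets of rules, follows the result to the response categories, and then sizes the effect.

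**Step 1: classify example lesions.** The 3.1 test is longest diameter at least 10 mm on CT. The section 12 test is short axis above 15 mm for a node. For a non-nodal lesion it is above 10 mm on slices up to 5 mm, and at least 2 x slice thickness on thicker slices.

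| Lesion | 3.1 item 2 | 12.2 / 12.3 |
|---|---|---|
| Node 18 x 12 mm | eligible | 12 is not above 15: non-measurable |
| Node 20 x 14.9 mm | eligible | 14.9 is not above 15: non-measurable |
| Node 20 x 16 mm | eligible | measurable |
| Non-nodal 12 mm, 7 mm slices | eligible | minimum 2 x 7 = 14: non-measurable |
| Non-nodal 14 mm, 7.5 mm slices | eligible | minimum 2 x 7.5 = 15: non-measurable |
| Non-nodal 12 mm, 5 mm slices | eligible | measurable |

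**Step 2: follow the result through.** No measurable lesion means no target lesion (12.2). Without a target lesion there is no target sum, so neither PR nor the 20% PD rule can be met (12.4.1). The non-measurable table in 12.4.3 applies, and 5.5.4 does not remove the patient from the denominator.

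**Step 3: size the effect on ORR.** Inputs: N = 36 (5.4 and 14.1). The documents give neither k, the number of patients without a target lesion, nor the response rate p in the others. I assume p = 20%, no CR among the k patients, and k from 1 to 6.

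- Ceiling per patient: 1/36 = 2.8 points.
- Expected loss per patient: 0.20/36 = 0.6 points.
- ORR over 36 = 0.20 x (36 - k)/36.

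| k | Able to score PR | ORR over 36 |
|---|---|---|
| 0 | 36 | 20.0% |
| 1 | 35 | 19.4% |
| 2 | 34 | 18.9% |
| 4 | 32 | 17.8% |
| 6 | 30 | 16.7% |

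At the interim look the ceiling is 1/10 = 10 points per patient. At the same assumed 20% the expected loss is 0.20/10 = 2 points.

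**Step 4: test the direction.** The no-CR assumption in step 3 need not hold. Under 12.4.2 a non-target node meets the CR size rule below 10 mm short axis. A sole 12 mm node gets there with shrinkage just over (12 - 10)/12 = 16.7%, less than the 30% needed for a target-lesion PR, provided the tumor marker is normal. For that patient, scoring a response could be easier rather than harder.

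**Step 5: test the effect on PFS.** New lesions and unequivocal non-target progression count as PD in both 12.4.3 tables, and death counts for everyone (12.4.5). Only the sum rule is lost. Because that rule also needs a 5 mm absolute increase, a sole 12 mm target lesion would have to grow by 5/12 = 41.7% to trigger it.

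**The case against.** The strongest reply is that 12.2 supplies the detail behind 3.1: it defines the same term in similar opening words, and 12.1 applies RECIST 1.1 to response and progression. An experienced investigator may well read it that way. But 3.1 states a complete definition with its own numbers and no cross-reference, so a checklist taken from it would be faithful to the text and still admit these patients.

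The second reply is rarity, and much of it stands. The patient's only disease must be a small node, or a small lesion on thick slices; one other measurable lesion removes the problem. This is a single-institution study. Section 12.2 recommends slices of 5 mm or less for nodes, 12.3 assumes that thickness, and nothing shows that thicker slices are used.

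The third reply is that nobody is left unscorable, since 12.4.3 has a table for non-measurable disease. That is true, but the table has no PR row.

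Three stronger readings are tempting and are not supported:
- A reader might infer that each such patient lowers ORR by 2.8 points. That is the ceiling, reached only if the patient would certainly have responded, and CR remains open.
- A reader might infer that these patients will look progression-free for longer. Most routes to PD are unchanged, and the documents give nothing from which a longer PFS could be shown.
- A reader might infer that a node of exactly 15 mm falls in no class. The residual wording of 12.2 makes it non-measurable.

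The difference between at-least and greater-than signs may be typographic (12.3 itself uses at least 10 mm for calipers), and 12.3 accepts MRI in certain situations. The point does not depend on either.

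**Conclusion.** The conflict is real: a patient can satisfy inclusion 2 and have no target lesion under section 12. PR and target-sum PD are then unavailable, while the patient stays in the response denominator. The main effect is on ORR, the interim look and the response-biomarker analyses. PFS remains scorable through non-target progression, new lesions or death.

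The size is modest: at most 2.8 points of a 36-patient ORR per patient, and about 0.6 points expected if the response rate were 20%. That rate is an assumption. So is any count of affected patients, which the documents do not give and which is probably small. The direction is not certain, because CR stays possible and may be reached with less nodal shrinkage than PR requires. The case for correcting it is that eligibility and measurement should use one definition and the correction is cheap; no large bias has been shown.

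**What to change.** Reword inclusion criterion 2 to require at least one measurable lesion as defined in 12.2 and 12.3, including the short-axis rule for lymph nodes and the slice-thickness rule. In the same amendment, reconcile the at-least and greater-than cut-offs across 3.1, 12.2 and 12.3, and list MRI consistently in all three.

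The cost is amendment wording and one line of the eligibility checklist. The downside is that an occasional patient with only small nodal disease, or only a small lesion on thick slices, becomes ineligible.

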### 3.2 Exclusion Criteria

1. Chemotherapy < 2 weeks prior to the first planned dose of study treatment.
2. Radiotherapy < 3 weeks prior to the first planned dose of study treatment.
3. A history of other malignancy  $\leq$  2 years previous with the exception of basal cell or squamous cell carcinoma of the skin which were treated with local resection only or carcinoma *in situ* of the cervix.
4. Currently receiving any other investigational agents.
5. Known brain metastases. Patients with known brain metastases must be excluded from this clinical trial because of their poor prognosis and because they often develop progressive neurologic dysfunction that would confound the evaluation of neurologic and other adverse events.
6. A history of allergic reactions attributed to compounds of similar chemical or biologic composition to tosedostat or capecitabine or other agents used in the study.
7. Previous treatment with any aminopeptidase inhibitor.
8. Previous exposure to either 5-FU or capecitabine at a systemic dose except for use in concurrent chemoradiation.
9. Known dihydropyrimidine dehydrogenase (DPD) deficiency or severe renal impairment (creatinine clearance < 30 mL/min by Cockcroft-Gault formula), as this would preclude use of capecitabine.
10. Significant cardiovascular disease defined as:
  - a. Myocardial infarction within 6 months of screening.
  - b. Unstable angina pectoris
  - c. Uncontrolled or clinically significant arrhythmia Grade  $\geq$  2
  - d. LVEF below institutional limits at screening
  - e. Congestive heart failure NYHA class III or IV
  - f. Presence of clinically significant valvular heart disease
11. Baseline troponin I or T > IULN and b-type natriuretic peptide > IULN.
12. Prior exposure to cardiotoxic agent, such as anthracyclines, within 3 months of enrollment.
13. Patient must have a QTc interval on ECG  $\leq$  0.48 seconds by Bazett's calculation at screening.

14. Patient may not be taking any drugs that prolong the QT/QTc interval (see Appendix C). If patient is on any of these drugs, patient may enroll in the study if the drugs can be discontinued for at least 5 half-lives prior to the first dose of tosedostat and capecitabine.
15. Uncontrolled intercurrent illness including, but not limited to, ongoing or active infection or psychiatric illness/social situations that would limit compliance with study requirements.
16. Pregnant and/or breastfeeding. Patients that are of childbearing age must have a negative pregnancy test at screening and agree on using contraception during the duration of the study.
17. Known HIV-positivity on combination antiretroviral therapy because of the potential for pharmacokinetic interactions with tosedostat or capecitabine. In addition, these patients are at increased risk of lethal infections when treated with marrow-suppressive therapy. Appropriate studies will be undertaken in patients receiving combination antiretroviral therapy when indicated.

### **3.3 Inclusion of Women and Minorities**

Both men and women and members of all races and ethnic groups are eligible for this trial.

## **4.0 REGISTRATION PROCEDURES**

**Patients must not start any protocol intervention prior to registration through the Siteman Cancer Center.**

The following steps must be taken before registering patients to this study:

1. Confirmation of patient eligibility
2. Registration of patient in the Siteman Cancer Center OnCore database
3. Assignment of unique patient number (UPN)

### **4.1 Confirmation of Patient Eligibility**

Confirm patient eligibility by collecting the information listed below:

1. Registering MD's name
2. Patient's race, sex, and DOB
3. Three letters (or two letters and a dash) for the patient's initials
4. Copy of signed consent form
5. Completed eligibility checklist, signed and dated by a member of the study team
6. Copy of appropriate source documentation confirming patient eligibility

## **4.2 Patient Registration in the Siteman Cancer Center OnCore Database**

All patients must be registered through the Siteman Cancer Center OnCore database.

## **4.3 Assignment of UPN**

Each patient will be identified with a unique patient number (UPN) for this study. All data will be recorded with this identification number on the appropriate CRFs.

## **5.0 TREATMENT PLAN**

This is a single institution phase I/II study combining tosedostat, an aminopeptidase inhibitor, with capecitabine. The study aims to determine the recommended phase 2 dose (RP2D) of tosedostat when given with a standard dose of capecitabine (1000 mg/m^2 BID) and to evaluate the preliminary efficacy of tosedostat and capecitabine combination therapy in advanced or metastatic pancreatic adenocarcinoma.

The phase I study will be conducted in a standard 6-patient-per-cohort dose de-escalation fashion. For the phase II part of the study, the primary endpoint of the study is to assess the progression-free survival (PFS) of the combination therapy. The dose of tosedostat used in phase II of this study will be determined during the phase I dose de-escalation portion.

### **5.1 Premedication Administration**

No premedications are required for either capecitabine or tosedostat. Anti-nausea medications can be used as per the treating physician's discretion.

### **5.2 Agent Administration**

Tosedostat is an oral drug which will be taken on an outpatient basis daily on a 21-day cycle. Patients should take tosedostat at approximately the same time every day (preferably morning) with a glass of water after food. If a patient misses a dose by more than 6 hours, the patient should be instructed not to take or make up that dose and to resume dosing with the next scheduled dose. Patients will be instructed to bring all unused drug and their medication diary (Appendix B) to each study visit for assessment of compliance. Dosing of tosedostat during phase I will be as described in Section 5.4. Dosing of tosedostat during phase II will be the dose determined during phase I.

Capecitabine is an oral drug which will be taken on an outpatient basis at a dose of 1000 mg/m^2 twice a day on Days 1 through 14 of a 21-day cycle. The tablets are to be swallowed with water and taken 30 minutes after the end of a meal. If the patient vomits or misses a dose by more than 2 hours, s/he must not take the missed dose and must not double the next dose. Instead, s/he should continue with the dosing as scheduled.

Patients will be instructed to bring all unused tablets and medication diary (Appendix B) to each study visit for assessment of compliance.

### 5.3 Dose De-Escalation Schema

| Dose Escalation Schedule |                                            |                                            |
|---------------------------------|--------------------------------------------|--------------------------------------------|
| Dose Level               | Tosedostat (PO daily)
Days 1-21 | Capecitabine (PO BID)
Days 1-14 |
| Level 0 (Starting dose)         | 120 mg                                     | 1000 mg/m                      |
| Level -1                        | 60 mg                                      |                                            |

### 5.4 Phase II Treatment Plan

Once the RP2D is determined, additional patients will be enrolled for a total of 36 evaluable patients (the patients from the RP2D level of phase I will be included in this group).

### 5.5 Definition of RP2D, DLT, Dose De-Escalation Criteria, and Toxicity, Response, and DLT Evaluations

#### 5.5.1 Definition of Recommended Phase 2 Dose (RP2D)

The recommended phase 2 dose (RP2D) is defined as the dose level immediately below the dose level at which 2 patients of a cohort (of 2 to 6 patients) experience dose-limiting toxicity during the first cycle. If 0 or 1 of 6 patients in Dose Level 1 experience DLT during the first cycle, Dose Level 1 will be presumed to be the RP2D.

#### 5.5.2 Dose Limiting Toxicities (DLTs)

Hematologic DLT is defined as any of the following that occur during the first cycle that are attributed as possibly, probably, or definitely related to the study treatment:

- Grade 4 neutropenia > 7 day duration
- Febrile neutropenia of any duration with temperature  $\geq 38.5$  °C
- Grade 4 anemia which requires transfusion therapy on more than two occasions in 7 days
- Grade 4 thrombocytopenia

Non-hematologic DLT is defined as any possibly, probably, or definitely related grade 3 or grade 4 non-hematologic toxicity that occurs during the first cycle with the following specific EXCEPTIONS:

- Grade 3 nausea, vomiting, diarrhea, or anorexia lasting no more than 72 hours that returns to Grade 1 prior to the start of Cycle 2
- Grade 3 hand-foot syndrome will only be considered a DLT for patients who have received one week of supportive care treatment with no

improvement

- Grade 3 fatigue that returns to Grade 1 prior to the start of Cycle 2
- Grade 3 flu-like symptoms lasting no more than 72 hours that returns to Grade 1 prior to start of Cycle 2
- Grade 3 arthralgia or myalgias lasting no more than 72 hours that return to Grade 1 prior to the start of Cycle 2
- Grade 3 potassium, phosphorus, or magnesium that is asymptomatic or of non-clinical significance lasting no more than 72 hours
- Grade 3 hypoalbuminemia

